7.4. Criteria for Study Termination

This study may be prematurely terminated, if in the opinion of the Sponsor, there is sufficiently reasonable cause. In the event of such action, written notification documenting the reason for study termination will be provided to each Investigator.

The study will be terminated if any of the following circumstances occur:

- Determination of unexpected, significant, or unacceptable risk to subjects. (An IDMC will review the safety data on a regular basis to ensure the risk/benefit ratio.)
- Failure to enter subjects at an acceptable rate.
- Insufficient adherence to protocol requirements.
- Plans to modify, suspend, or discontinue the development of the study treatment.
- Other administrative reasons.

If the study is terminated early for any reason other than unacceptable toxicity, Sponsor will continue to provide drug to subjects who are benefiting from treatment. Should the study be closed prematurely due to unacceptable toxicity, all study materials must be returned to the Sponsor or Sponsor's designee.

8. STUDY POPULATION

8.1. Number of Subjects

A total of approximately 186 subjects will be randomized in a 2:1 ratio, stratified by number of prior systemic treatment regimens for advanced disease (1 or 2) into the 2 treatment arms, including approximately 124 subjects in the AG-120 arm and 62 subjects in the placebo arm.

8.2. Inclusion Criteria

Subjects must meet all of the following criteria to be enrolled in the study:

1. Be ≥ 18 years of age.
2. Have a histopathological diagnosis (fresh or banked tumor biopsy sample, preferably collected within the last 3 years) consistent with nonresectable or metastatic cholangiocarcinoma and are not eligible for curative resection, transplantation, or ablative therapies.
3. Have documented IDH1 gene-mutated disease (from a fresh tumor biopsy or the most recent banked tumor tissue available) based on central laboratory testing (R132C/L/G/H/S mutation variants tested).
4. Have an ECOG PS score of 0 or 1 (Appendix 15.1).
5. Have an expected survival of ≥ 3 months.
6. Have at least one evaluable and measurable lesion as defined by RECIST v1.1. Subjects who have received prior local therapy (including but not limited to embolization, chemoembolization, radiofrequency ablation, or radiation therapy) are eligible provided measurable disease falls outside of the treatment field or within the field and has shown $\geq 20\%$ growth in size since post-treatment assessment.
7. Have documented disease progression following at least 1 and no more than 2 prior systemic regimens for advanced disease (nonresectable or metastatic). Subjects must have received at least 1 gemcitabine- or 5-FU-containing regimen for advanced cholangiocarcinoma. Systemic adjuvant chemotherapy will be considered a line of treatment if there is documented disease progression during or within 6 months of completing the therapy.
8. Have recovered from toxicities associated with prior anticancer therapy to baseline unless stabilized under medical management.
9. Have adequate bone marrow function as evidenced by:
 - a. Absolute neutrophil count $\geq 1,500/\text{mm}^3$ or $1.5 \times 10^9/\text{L}$
 - b. Hemoglobin ≥ 8 g/dL
 - c. Platelets $\geq 100,000/\text{mm}^3$ or $100 \times 10^9/\text{L}$
10. Have adequate hepatic function as evidenced by:
 - a. Serum total bilirubin $\leq 2 \times$ upper limit of normal (ULN), unless considered due to Gilbert's disease
 - b. Aspartate aminotransferase (AST) and alanine aminotransferase (ALT) $\leq 5 \times$ ULN

11. Have adequate renal function as evidenced by:
 - a. Serum creatinine $<1.5 \times \text{ULN}$

OR

 - b. Creatinine clearance ≥ 50 mL/min based on the Cockcroft-Gault glomerular filtration rate (GFR) estimation:
$$(140 - \text{Age}) \times (\text{weight in kg}) \times (0.85 \text{ if female}) / 72 \times \text{serum creatinine}$$
12. Be able to understand and willing to sign the informed consent form and to comply with scheduled visits, treatment plans, procedures, and laboratory tests, including serial peripheral blood sampling and urine sampling, during the study. A legally authorized representative may consent on behalf of a subject who is otherwise unable to provide informed consent if acceptable to and approved by the site's Institutional Review Board (IRB)/Independent Ethics Committee (IEC). (Subjects who do not speak one of the languages that the QLQ-C30, QLQ-BIL21, PGI-C, PGI-S, or EQ-5D-5L are provided in at this time will be permitted to enroll and not complete these HRQOL/health economic outcome instruments, assuming all other eligibility criteria are met.)
13. Female subjects with reproductive potential must have a negative serum pregnancy test prior to the start of therapy, or a confirmation from an obstetrician in case of equivocal serum pregnancy results. Females of reproductive potential are defined as sexually mature women who have not undergone a hysterectomy, bilateral oophorectomy, or tubal occlusion or who have not been naturally postmenopausal (ie, who have not menstruated) for at least 24 consecutive months (ie, have not had menses at any time in the preceding 24 consecutive months). Women of reproductive potential, as well as fertile men with partners who are female with reproductive potential, must agree to use 2 effective forms of contraception (including at least 1 barrier form) from the time of giving informed consent throughout the study and for 90 days (both females and males) following the last dose of study drug. Effective forms of contraception are defined as hormonal oral contraceptives, injectables, patches, intrauterine devices, intrauterine hormone-releasing systems, bilateral tubal ligation, condoms with spermicide, or male partner sterilization.

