8.3. Exclusion Criteria

Subjects who meet any of the following criteria will not be enrolled in the study:

1. Received a prior IDH inhibitor.
2. Received systemic anticancer therapy or investigational agent <2 weeks prior to Day 1 (washout from prior immune based anticancer therapy is 4 weeks). In addition, the first dose of study treatment should not occur before a period ≥ 5 half-lives of the investigational agent has elapsed.
3. Received radiotherapy to metastatic sites of disease <2 weeks prior to Day 1.
4. Underwent hepatic radiation, chemoembolization, and radiofrequency ablation <4 weeks prior to Day 1.
5. Have known symptomatic brain metastases requiring steroids. Subjects with previously diagnosed brain metastases are eligible if they have completed their treatment and have

recovered from the acute effects of radiation therapy or surgery prior to study entry, have discontinued corticosteroid treatment for these metastases for at least 4 weeks and have radiographically stable disease for at least 3 months prior to study entry. Note: up to 10 mg per day of prednisone equivalent will be allowed.

6. Have a history of another primary cancer, with the exception of: a) curatively resected non-melanoma skin cancer; b) curatively treated cervical carcinoma in situ; or c) other primary solid or liquid tumor with no known active disease present that, in the opinion of the Investigator, will not affect subject outcome in the setting of current cholangiocarcinoma diagnosis.
7. Underwent major surgery within 4 weeks of Day 1 or have not recovered from post-surgery toxicities.
8. Are pregnant or breastfeeding.
9. Are taking known strong CYP3A4 inducers or sensitive CYP3A4 substrate medications with a narrow therapeutic window (Appendix 15.2), unless they can be transferred to other medications within ≥ 5 half-lives prior to dosing.
10. Exclusion criterion 10 removed in Protocol Amendment 4, Version 5.0.
11. Have an active infection requiring systemic anti-infective therapy or with an unexplained fever $>38.5^{\circ}\text{C}$ within 7 days of Day 1 (at the discretion of the Investigator, subjects with tumor fever may be enrolled).
12. Have any known hypersensitivity to any of the components of AG-120 or the matched placebo.

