8.5.1. Withdrawal from Study Treatment

Subjects may discontinue or be discontinued from study treatment at any time. In this situation, a subject without documented progressive disease by the Investigator should be followed for tumor

assessments until the development of progressive disease and/or survival. Subjects will be discontinued from study treatment for the following reasons:

- Withdrawal of consent
- Certain adverse events (as described in Section 9.8) including instances of Grade 4 QTcF prolongation
- A confirmed diagnosis of PML (Section 11.3.1) or Guillain-Barre syndrome (Section 11.3.2)
- Disease progression (subjects who are, in the opinion of the Investigator, benefitting from treatment [eg, slow progression] may be allowed to continue on study treatment with approval of the Medical Monitor)
- Death
- Investigator decision
- Subject decision to withdraw from treatment (subject may continue with PFS and/or survival follow-up)
- Protocol violation: non-adherence to study treatment regimen or protocol requirements
- Confirmed pregnancy (study therapy should be immediately interrupted based upon a positive urinary human chorionic gonadotropin [hCG] test, and permanently discontinued if confirmed by a serum β -hCG test)
- Lost to follow-up

All AEs should be followed until resolution or for a period of 28 days from the last dose of study treatment, whichever is shorter. If the subject withdrew from treatment because of an AE, every effort must be made to perform protocol-specified safety follow-up procedures.

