9.13.4. Drug-Drug Interactions

AG-120 is mainly metabolized by CYP3A4 and, therefore, subjects should not use strong CYP3A4 inducers (Appendix 15.2) during treatment with AG-120.

AG-120 clinical trials and physiologically based pharmacokinetic (PBPK) simulations have shown that AG-120 plasma concentrations increase with co-administration of a strong or moderate CYP3A4 inhibitor, and increased AG-120 plasma concentrations may increase the risk of QTc prolongation. Therefore, alternative therapies that are not strong or moderate CYP3A4 inhibitors should be considered during treatment with AG-120. If concomitant use of strong or moderate CYP3A4 inhibitors is unavoidable, subjects should be monitored for increased risk of QTc prolongation.

AG-120 is an inducer of human CYP3A4/5 and may also induce CYP2B6, CYP2C8, and CYP2C9. Therefore, medications of sensitive CYP3A4 substrates with a narrow therapeutic window (Appendix 15.2) should be avoided unless the subject can be transferred to other medications prior to enrolling. Consider alternative therapies that are not sensitive substrates of CYP2C9 (eg, phenytoin, warfarin). Monitor international normalized ratio (INR) levels more frequently in subjects receiving warfarin (a CYP2C9 substrate) during initiation or discontinuation of AG-120.

AG-120 is an inhibitor of OAT3. A PBPK simulation predicted an increase (<30%) in the AUC of a sensitive OAT3 substrate, suggesting that the potential for clinically relevant drug interactions due to the inhibition of OAT3 appears to be low.

Coadministration of AG-120 may decrease the concentrations of hormonal contraceptives.

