- ¹¹ Sodium, potassium, calcium, magnesium, phosphorus, albumin, glucose, blood urea nitrogen (BUN), creatinine, uric acid, lactate dehydrogenase (LDH), alkaline phosphatase (ALP), alanine aminotransferase (ALT), aspartate aminotransferase (AST), total bilirubin, and direct bilirubin. No need to repeat on C1D1

if baseline assessment performed within 3 days prior to that date, or on cross over C1D1 if EOT assessment performed within 3 days prior to that date. CA19-9 will also be collected at Screening, C1D1, Day 1 of every other cycle, and at EOT. No need to repeat CA19-9 on C1D1 or cross over C1D1 if an assessment was performed within 3 days prior to that date. On C1D1 and cross over C1D1, assessments should be conducted pre-dose.

¹² Prothrombin time (PT), activated partial thromboplastin time (aPTT), and international normalized ratio (INR).

¹³ Color, appearance, pH, specific gravity, ketones, protein, glucose, bilirubin, nitrite, urobilinogen, occult blood, and microscopic inspection of sediment.

¹⁴ A serum pregnancy test will be performed at Screening and a urine pregnancy test will be conducted on C1D1 and confirmed negative prior dosing, and on Day 1 of all subsequent cycles. On C1D1 and cross over C1D1, the test should be conducted pre-dose.

¹⁵ Assign subject number and randomization allocation for eligible subjects.

¹⁶ The morning doses on C1D1, C1D15, C2D1, C3D1, and Day 1 of all subsequent cycles are to occur in clinic to allow for pre-dose assessments (C1D1) and to accommodate PK/PD sampling (see Section 10.8 and Section 10.9).

¹⁷ Treatment compliance is to be assessed based on return of unused drug as well as subject diaries (see Section 9.11).

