Females of reproductive potential must have a negative serum pregnancy test prior to the start of therapy, or a confirmation from an obstetrician in case of equivocal serum pregnancy results. Women of reproductive potential, as well as fertile men with partners who are female with reproductive potential, must agree to use 2 effective forms of contraception (including at least 1 barrier form) from the time of giving informed consent throughout the study and for 90 days (both females and males) following the last dose of study drug. Females of reproductive potential are defined as sexually mature women who have not undergone a hysterectomy or bilateral oophorectomy or who have not been naturally postmenopausal (ie, who have not menstruated at all) for at least 24 consecutive months (ie, has had menses at any time in the preceding 24 consecutive months).

Males with partners who are female with reproductive potential must agree that they or their partners will use 2 effective forms of contraception (including at least 1 barrier form) when

engaging in reproductive sexual activity throughout the study and will avoid conceiving for 90 days after the last dose of study treatment.

Effective forms of contraception are defined as hormonal oral contraceptives, injectables, patches, intrauterine devices, intrauterine hormone-releasing systems, bilateral tubal ligation, condoms with spermicide, or male partner sterilization. Please refer to Section 9.13.4 for further details on potential drug-drug interactions with hormonal contraceptives.

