15.2. Prohibited Concomitant Medications

Prohibited medications and certain foods are not allowed in this study while subjects are receiving study drug.	
Strong CYP3A Inducers	CYP3A Substrates with a Narrow Therapeutic Window
Avasimibe, carbamazepine, enzalutamide, mitotane, phenytoin, rifampin, rifabutin, St. John's wort	Alfentanil, astemizole ¹ , cyclosporine, dihydroergotamine, ergotamine, fentanyl, pimozone, quinidine, everolimus, sirolimus, tacrolimus, terfenadine ¹

Note that this is not an exhaustive list. For an updated list, see the following link:

<http://www.fda.gov/Drugs/DevelopmentApprovalProcess/DevelopmentResources/DrugInteractionsLabeling/ucm080499.htm>

“CYP substrates with a narrow therapeutic window” refers to drugs whose exposure-response relationship indicates that small increases in their exposure levels by the concomitant use of CYP inhibitors may lead to serious safety concerns (eg, Torsades de Pointes).

¹ Withdrawn from the United States market because of safety reasons.

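### Criterion 13 accepts hormonal contraceptives as an effective second form without qualification, although Section 9.13.4 warns that AG-120 may lower their levels and gives no instruction

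*Protocol*

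**What the plan says.** Criterion 13 (Protocol Section 8.2, repeated in the Synopsis) applies to women of reproductive potential and to fertile men with such partners. Each "must agree to use 2 effective forms of contraception (including at least 1 barrier form"), from consent until 90 days after the last dose. The definition begins "Effective forms of contraception are defined as hormonal oral contraceptives, injectables, patches" and goes on to intrauterine devices, hormone-releasing intrauterine systems, tubal ligation, condoms with spermicide and a sterilized male partner. Nothing separates hormonal from non-hormonal methods.

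Section 9.13.4 describes AG-120 as an inducer of CYP3A4/5 and possibly of three further CYP enzymes. It ends with one sentence on contraception: "Coadministration of AG-120 may decrease the concentrations of hormonal contraceptives".

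Section 11.4 restates the two-method requirement and the same list, then adds: "Please refer to Section 9.13.4 for further details on potential drug-drug interactions with hormonal contraceptives". The pointer is absent from criterion 13 and from the Synopsis.

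On monitoring, there is a serum pregnancy test at Screening and a urine test on C1D1, "confirmed negative prior dosing, and on Day 1 of all subsequent cycles" (Table 3, footnote 14). If a test is positive, "study therapy should be immediately interrupted based upon a positive urinary human chorionic gonadotropin" (Section 8.5.1).

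**The concern.** The protocol sets two effective methods as its standard and then, elsewhere, casts doubt on one class of method that it counts towards the two. An investigator who checks eligibility from Section 8.2 alone would not see the doubt. One who follows the pointer from Section 11.4 would find a warning but nothing that changes which combinations are acceptable.

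What is at stake is subject safety, namely the margin against an unintended pregnancy during treatment with an investigational drug. The statistical plan is not involved: the SAP only lists pregnancy test results (Section 9.4.6), and no estimate, test or sample size depends on this rule.

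**Working it through.** The documents give no figure to reproduce, so this is a comparison of texts.

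**1. What counts as compliant.** Criterion 13 names eight forms. Reading injectables and patches as hormonal products, they divide as follows:

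- systemic hormonal: oral, injectable, patch (3)
- hormone-releasing intrauterine system (1)
- barrier: condoms with spermicide (1)
- other non-hormonal: intrauterine device, tubal ligation, sterilized male partner (3)

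3 + 1 + 1 + 3 = 8. Any one of the systemic hormonal forms plus condoms with spermicide makes two listed forms including one barrier, so the criterion is met.

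**2. What the interaction warning touches.** Section 9.13.4 refers to hormonal contraceptives in general. Of the two methods in step 1, the hormonal one falls under the warning and the barrier does not. That leaves 2 − 1 = 1 method outside the stated interaction.

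**3. Whether Section 9.13.4 supplies an instruction.** For its other interactions it either acts or explains why no action is needed:

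- strong CYP3A4 inducers: not to be used
- strong or moderate CYP3A4 inhibitors: consider alternatives, otherwise monitor QTc
- sensitive CYP3A4 substrates with a narrow window: avoid
- CYP2C9 substrates: consider alternatives, and check INR more often with warfarin
- OAT3 substrates: predicted change small, clinical relevance judged low
- hormonal contraceptives: no action and no assessment of relevance

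**4. Whether another rule closes the gap.** Exclusion 9 bars subjects who "Are taking known strong CYP3A4 inducers or sensitive CYP3A4 substrate medications with a narrow therapeutic window". Appendix 15.2 explains that class as drugs for which "small increases in their exposure levels by the concomitant use of CYP inhibitors may lead to serious safety concerns". That is harm from too much exposure, whereas the contraceptive problem would be too little. The appendix list, which is stated to be incomplete, names no contraceptive. The Medical Monitor confirms eligibility before randomization (Section 8.4), but against criterion 13 as written.

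**5. Who is concerned.** The women concerned are those who take AG-120, whether randomized to it or after crossover. Female partners of male subjects do not take the drug, so the warning does not reach their methods. The two-method rule nevertheless covers male subjects too. It therefore reads as a general standard, not as an allowance already made for this interaction.

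**The case against.** The strongest reply is that the protocol already manages the hazard. No woman may rely on hormones alone, because a barrier is compulsory until 90 days after the last dose. Section 11.4, where contraception and pregnancy are handled, directs the investigator to the interaction. Pregnancy is tested at Screening, before the first dose and every cycle, and a positive test interrupts treatment. The Investigator's Brochure, to which Sections 5.3.2 and 5.4 refer for detail, and the consent form are natural places for contraceptive counselling. Neither was available here. How strictly to treat a possible interaction when a barrier is mandatory is partly a matter of judgement.

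Most of this stands, and it is why the point is minor. It does not remove the inconsistency. The pregnancy tests detect but do not prevent, and neither the pointer nor the Medical Monitor's check alters what the criterion accepts. Advice in the Brochure or consent form, if it exists, would be a reason to align criterion 13 with it.

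Three stronger readings are tempting, and the documents do not support them:

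- A reader might infer that AG-120 makes hormonal contraception fail. Section 9.13.4 says only that levels may fall. It gives neither the size of the fall nor any effect on contraception.
- A reader might infer a fetal hazard from the absence of an embryo-fetal study in Section 5.3.2.2. That section belongs to an explicit summary, with details in the Brochure, so the absence shows nothing either way.
- A reader might try to size the problem from the drug's half-life and the lack of a scheduled pregnancy test at the EOT or safety follow-up visit. Those features apply equally to women using any method, so they do not measure this inconsistency. The half-lives in Section 5.3.3.1 are preliminary means across dose levels, and dose holds would alter any interval built on them.

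**Conclusion.** The inconsistency is real. Criterion 13, its Synopsis copy and Section 11.4 count as fully effective a class of method that Section 9.13.4 says AG-120 may weaken, and no instruction reconciles them. For a woman using a systemic hormonal method plus a barrier, one of her two required methods lies outside the stated interaction.

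The residual risk is limited by the safeguards already in place. It cannot be quantified, because the documents do not give the number of women of reproductive potential, their choice of methods, the size of the interaction or its contraceptive consequence.

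The conclusion assumes that injectables and patches in the list are hormonal and that no instruction outside the two documents already governs the matter. Whether hormone-releasing intrauterine systems are affected is left open: taken literally, the warning covers them, but the documents do not say whether the interaction matters for them. No endpoint, sample size or analysis is touched. This is a cheap improvement of minor severity.

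**What to change.** Add one rule to criterion 13 (Section 8.2 and Synopsis) and to Sections 11.4 and 9.13.4, for example:

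> Because AG-120 may lower the levels of hormonal contraceptives, female subjects of reproductive potential in either arm should not rely on a hormonal oral, injectable or patch method as the second effective form. They should use a non-hormonal second form together with the barrier. If none is feasible, a hormonal method plus the barrier may be used after documented counselling on the interaction.

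The rule covers both arms because treatment is blinded and placebo subjects must still meet the eligibility criteria to cross over (Section 7.1). Two clarifications should go with it. The sponsor should state whether hormone-releasing intrauterine systems are affected. The text should also say that hormonal methods used by female partners of male subjects still count.

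The cost is a short text change in four places, with written IRB/IEC approval (Section 13.5) across about 55 centers, and matching consent wording if it is not already there. Some women will have to change or add a method. The counselling fallback matters because the list is short: apart from the barrier, its non-hormonal forms are an intrauterine device, tubal ligation and a sterilized partner, and Section 8.2 already places women with tubal occlusion outside the definition of reproductive potential. With the fallback, no woman is delayed or excluded solely because a non-hormonal second form is not feasible.
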